### 7.4 Study Schedule

Table 2: Study Schedule

Procedures	Screening Visit	Final Screening/Procedure Visit	2 week Post-Procedure Visit (± 1.5 weeks)	3 μ , 6 Λ , 12 and 18 Months Post-Procedure Visit (± 16 weeks)	24 Months Post-Procedure Visit (± 16 weeks)	36 Months Post-Procedure Visit (± 16 weeks)	48 Months Post-Procedure Visit (± 16 weeks)	60 Months Post-Procedure Visit (± 16 weeks)	Unscheduled Visit
Number of Visit	Visit 1	Visit 2	Visit 3	Visits 4-7	Visit 8	Visit 9	Visit 10	Visit 11	
Obtain Informed Consent	X								

 CartiHeal	A Post Approval Multicenter Open-label Randomized Controlled Trial of Agili-C™ vs. Surgical Standard of Care (SSOC) for the Treatment of Joint Surface Lesions of the Knee							
	CLN0021-US Rev. 8 March 29, 2022							

Procedures	Screening Visit	Final Screening/Procedure Visit	2 week Post-Procedure Visit ( $\pm 1.5$ weeks)	3 μ , 6 ^ , 12 and 18 Months Post-Procedure Visit ( $\pm 16$ weeks)	24 Months Post-Procedure Visit ( $\pm 16$ weeks)	36 Months Post-Procedure Visit ( $\pm 16$ weeks)	48 Months Post-Procedure Visit ( $\pm 16$ weeks)	60 Months Post-Procedure Visit ( $\pm 16$ weeks)	Unscheduled Visit
Assignment of Subject Number	X								
Review Inclusion/Exclusion criteria	X	X (intraoperative)							
BMI	X @								
Medical History	X								
Baseline MRI	X*								
MRI according to CartiHeal protocol				X**	X**	X"	X"	X"	X***
Defect Fill Evaluation according to MRI, off-site				X **,∞	X**				
Baseline standing X-ray (AP & Lateral)	X*								
Weight bearing AP & Lateral X-ray			X #	X ∞	X	X	X	X	X***
IKDC Knee Examination form 2000 (Surgeon)	X			X ∞	X	X	X	X	X ##
OA Classification Kellgren-Lawrence score, off-site	X								
ICRS Cartilage Injury Standard Evaluation Form 2000 (Subject)	X								

 CartiHeal	A Post Approval Multicenter Open-label Randomized Controlled Trial of Agili-C™ vs. Surgical Standard of Care (SSOC) for the Treatment of Joint Surface Lesions of the Knee							
	CLN0021-US Rev. 8 March 29, 2022							

Procedures	Screening Visit	Final Screening/Procedure Visit	2 week Post-Procedure Visit ( $\pm 1.5$ weeks)	3 μ , 6 ^ , 12 and 18 Months Post-Procedure Visit ( $\pm 16$ weeks)	24 Months Post-Procedure Visit ( $\pm 16$ weeks)	36 Months Post-Procedure Visit ( $\pm 16$ weeks)	48 Months Post-Procedure Visit ( $\pm 16$ weeks)	60 Months Post-Procedure Visit ( $\pm 16$ weeks)	Unscheduled Visit
ICRS Knee History Registration (Surgeon)	X								
SF-12 v2	X			X ∞	X	X	X	X	
2000 IKDC Subjective Knee Evaluation Form	X			X ∞	X	X	X	X	
KOOS Subscales	X			X ∞	X	X	X	X	
Tegner score	X			X ∞	X	X	X	X	
mICRS cartilage injury mapping and classification		X							
Arthroscopy and randomization		X							
Knee and AE related medication recording	X	X	X	X	X	X	X	X	
AEs/SAEs		X	X	X	X	X	X	X	X
Tissue biopsy with histology									X****
Video recording - Implantation procedure		X							

@ Weight and Height, only at screening

# X-ray may be performed lying down or standing, per patient comfort

\* Screening MRI and X-ray must not be older than 1 year

\*\* MRI and Defect Fill evaluation is performed at 12 and 24 months. Additionally, MRI will be performed at 3 and 6 months to an initial cohort of at least 25 patients per study groups to evaluate presence of cysts

A Post Approval Multicenter Open-label

Randomized Controlled Trial of Agili-C™ vs.

Surgical Standard of Care (SSOC) for the  
Treatment of Joint Surface Lesions of the Knee

CLN0021-US

Rev. 8

March 29, 2022

\*\*\* MRI and X-ray will be performed according to PI decision

\*\*\*\* According to PI decision if surgery is performed. The biopsy will be sent to a central lab.

^ The 3 month visit may take place ±2 weeks

^ The 6 month visit may take place ±12 weeks

∞ Not applicable for the 3 months visit

“ Optional MRI

## According to PI decision

## 7.5 Unscheduled Visit

Each time the subject returns to the study site, the PI (or designee) will solicit and record information about AEs, Knee and AE treatment related medications and therapies. All applicable procedures should be performed including MRI and X-ray (according to PI's decision).

### 7.5.1 Unscheduled Visit without Surgery

Unexpected symptoms might lead to an unexpected visit. In such visits, the following should be performed:

1. Investigator completes the IKDC Knee Examination Form 2000 (optional)
2. Knee and AE treatment related medication recording
3. Record AEs/SAEs

### 7.5.2 Unscheduled Visit with Surgery

In case of a secondary procedure, the following should be performed:

1. Investigator completes the IKDC Knee Examination Form 2000 (optional)
2. ICRS cartilage repair assessment form (if applicable)
3. Record AEs/SAEs
4. Knee related and/or AE related medication recording
5. Tissue and/or implant removal and histology (if relevant)
6. Video recording of the procedure with images captured (if applicable)

A Post Approval Multicenter Open-label

Randomized Controlled Trial of Agili-C™ vs.

Surgical Standard of Care (SSOC) for the  
Treatment of Joint Surface Lesions of the Knee

CLN0021-US

Rev. 8

March 29, 2022

The study protocol does not require a tissue biopsy. If clinically required, the tissue should be sent to a central lab for histological assessment as determined by the Sponsor. The Sponsor should be notified in advance and a Sponsor's representative will be allowed to participate in the procedure and film it.

### **7.6 Compliance with Protocol**

The PI is responsible for compliance with the protocol at the investigational site. The PI is also responsible for reporting all issues of protocol non-compliance to the respective IRB/EC and to the Sponsor. A representative of the Sponsor will make frequent contact with the PI and research staff and will conduct regular monitoring visits at the site to review subject and device accountability records for compliance with the protocol, e.g., subject eligibility criteria, randomization assignments, concomitant and subsequent procedures performed and follow-up visit schedule.

### **7.7 Discontinued Subjects**

The Principal Investigator will record on the CRF and will report to the Sponsor and the IRB/EC the reasons that subjects discontinue from the study, including subjects who sign the Informed Consent Form but do not proceed to randomization.

### **7.8 Study Termination**

If conditions arise during the study that indicate that the study or an investigational site should be terminated, the Sponsor will provide notification in accordance with 21 CFR and will advise the FDA, PIs, IRB/ECs, and appropriate institutional officials. The report will include the IDE number, the full name of the research protocol, the name(s) of the clinical investigators and the reason(s) for the suspension or termination.

Conditions that may warrant termination of the study or site include, but are not limited to:

1. Any unanticipated problems involving risks to human subjects or others

 CartiHeal	CLN0021-US-Investigational Plan A Post Approval Multicenter Open-label Randomized Controlled Trial of Agili-C™ vs. Surgical Standard of Care (SSOC) for the Treatment of Joint Surface Lesions of the Knee	Document Number: CLN-0000002 Document Version: 8.0 Effective Date: 08-Jun-2022 (GMT+2) Page 39 of 80
		CLN0021-US Rev. 8 March 29, 2022

2. Any instance of serious or continuing noncompliance with these regulations or the requirements or determinations of the IRB; or
3. Any suspension or termination of IRB approval
4. Study completion

### **7.9 Study Duration**

Study participation for an individual subject is expected to last up to 64 months, including the time to randomization and treatment (including arthroscopy) and the 60-month follow-up period. Study duration at each investigational site may last 6 to 7 years including recruitment phase, follow-up and close out. Study duration per patient will be up to 5 years total.

### **7.10 Documentation**

All tests will be performed prior to implantation procedure as required by the study protocol. Device handling will be recorded. The standard treatment and care provided to all subjects, alongside the application of the study device, will be performed and recorded in the subject's medical files and on the appropriate study CRF.

### **7.11 Deviations from Study Protocol**

Any deviations from the study protocol should be notified to the Sponsor, documented on study deviation forms, and reported to the IRB/EC as required by local regulations.

## **8.0 Safety and Medical Device Vigilance**

All adverse events occurring during the study will be recorded on the appropriate case report form page by the investigator. The nature, severity and relation of the adverse event to the study device will be documented. If an adverse event occurs, the first concern will be the safety of the study participants. All AEs occurring during the study will be followed throughout the study until resolved or stabilized or until follow-up is no longer possible.

A Post Approval Multicenter Open-label

Randomized Controlled Trial of Agili-C™ vs.

Surgical Standard of Care (SSOC) for the  
Treatment of Joint Surface Lesions of the Knee

CLN0021-US

Rev. 8

March 29, 2022

## 9.0 Definitions

### 9.1 Adverse Event (AE)

AE is defined as any untoward medical occurrence in a subject. This definition does not imply that there is a relationship between the adverse event and the device under investigation. An AE can therefore be any unintended sign, symptom, disease or injury or any untoward clinical signs (including an abnormal laboratory findings) in subjects, users or other persons whether or not related to the investigational medical device. The following should be reported as AE:

- Untoward medical conditions or signs or symptoms that were absent before starting study treatment.
- Untoward medical conditions or signs or symptoms present before starting study treatment and worsen (increase severity or frequency) after starting study treatment.
- Abnormal laboratory findings.
- Clinical signs or symptoms that require therapy.

### 9.2 Serious Adverse Events (SAE)

A SAE is an adverse event that:

- Led to a death
- Led to a serious deterioration in the health of the subject that:
  - Resulted in a life-threatening illness or injury.
  - Resulted in a permanent impairment of a body structure or a body function.
  - Required in-patient hospitalization or prolongation of existing hospitalization.
  - Resulted in medical or surgical intervention to prevent permanent impairment to body structure or a body function.
- Led to fetal distress, fetal death or a congenital abnormality or birth defect.

A Post Approval Multicenter Open-label  
Randomized Controlled Trial of Agili-C™ vs.  
Surgical Standard of Care (SSOC) for the  
Treatment of Joint Surface Lesions of the Knee

CLN0021-US  
Rev. 8  
March 29, 2022

Important medical events that may not result in death, be life-threatening, or require hospitalization may be serious when, based upon appropriate medical judgment, they may jeopardize the subject and may require medical or surgical intervention to prevent one of the outcomes listed above.

Inpatient hospitalization or prolongation of existing hospitalization means that hospital inpatient admission and/or prolongation of hospital stay were required for treatment of AE, or that they occurred as a consequence of the event. Hospitalization for elective treatment of a pre-study condition that did not worsen while on study and hospitalizations for treatment of non-adverse events (e.g. cosmetic surgery or diagnostic procedure) are not considered serious adverse events.

### **9.3 Adverse Events Classification**

AEs reported by the subject or observed by the investigator will be individually listed on an adverse event form in the CRF as follows: the specific event or condition, whether the event was present pre-study, the dates and times of occurrence, duration, severity, relationship to study device and/or procedure, specific countermeasures, and outcome.

Note: Event which was present pre-study is not considered as an adverse event unless it has worsened since the enrolment to the study.

All AEs will be characterized by the following criteria:

- Intensity or Severity
- Relatedness
- Outcome
- Treatment or Action Taken
- AEs and SAEs are recorded as of Enrolment

### **9.4 Intensity/Severity Definition**

The intensity or severity of the AE will be characterized as follows:

## A Post Approval Multicenter Open-label

Randomized Controlled Trial of Agili-C™ vs.

Surgical Standard of Care (SSOC) for the  
Treatment of Joint Surface Lesions of the Knee

CLN0021-US

Rev. 8

March 29, 2022

**Mild:** Transient or mild discomfort; no limitation in activity; no medical intervention/therapy required.

**Moderate:** Mild to moderate limitation in activity; some assistance may be needed; no or minimal medical intervention/therapy required.

**Severe:** Marked limitation in activity, some assistance usually required; medical intervention/therapy required, hospitalization possible.

## 9.5 Relationship to Investigative Device or SSOC

The Investigator and Medical Director will separately evaluate and document the relationship between an AE or SAE to the investigative device or the SSOC according to the parameters defined in Table 3. In case of disagreement between the investigator's evaluation and the Medical Director's evaluation, an independent evaluator, a physician, well versed in safety assessments of medical device clinical trials, will evaluate the case and determine the relationship between an AE or SAE to the investigative device or the treatment procedure.

**Table 3: Adverse Event Relationship Criteria**

Relationship	Criteria
Unrelated	The temporal sequence of the AE onset relative to treatment by the investigational device/SSOC is not reasonable. OR There is another obvious cause of the AE
Unlikely related	The relationship with the use of the device/SSOC can be reasonably explained by another cause, but additional information may be obtained.
Possibly related	The relationship with the use of the investigational device/SSOC is weak but cannot be ruled out completely. Alternative causes are also possible (e.g. an underlying or concurrent clinical condition or/and an effect of another device, or treatment)
Probably related	The relationship with the use of the investigational device/SSOC seems relevant and/or the event cannot reasonably explained by another cause, but additional information may be obtained.
Related	The AE can be explained only by the use of the investigational device/SSOC.

	A Post Approval Multicenter Open-label Randomized Controlled Trial of Agili-C™ vs. Surgical Standard of Care (SSOC) for the Treatment of Joint Surface Lesions of the Knee	CLN0021-US Rev. 8 March 29, 2022

Uncertain	The relationship between the AE and the device is uncertain
------------------	---

## 9.6 Outcome

The clinical outcome of the AE or SAE will be characterized as follows:

**Death** - The SAE CRF must be completed for this outcome.

**Recovered** - The patient returned to baseline status.

**Ongoing** - Patient did not recover and symptoms continue.

**Recovered with sequelae** - The patient has recovered but with clinical sequelae from the event.

**Unknown** - The patient outcome is unknown.

## 9.7 Treatment or Action Taken

The treatment or action taken after the occurrence of an AE or SAE will be reported as:

**Interventional Treatment** - Invasive intervention such as: surgery or intra-articular injection.

**Non-surgical intervention** - such as physical therapy

**Medical Treatment** - Medication initiated for event

**None** - No action is taken

## 9.8 SAE Reporting Requirements

### 9.8.1 Notification to the Sponsor: Initial and Follow-up

If the investigator identifies a SAE, a SAE report form must be completed and sent by email to the Sponsor and CartiHeal or entered into the eCRF within 24 hours of the investigator's knowledge of the event. Copies of hospital case reports (i.e., hospital progress notes, results of applicable diagnostic tests, lab results and biopsy results) should be sent as soon as they become available. Autopsy reports and other documents, as applicable, should be sent upon request.

**A Post Approval Multicenter Open-label Randomized Controlled Trial of Agili-C™ vs. Surgical Standard of Care (SSOC) for the Treatment of Joint Surface Lesions of the Knee**

CLN0021-US  
Rev. 8  
March 29, 2022

Reports should be made to the CartiHeal's Medical Director/Director of Clinical Affairs:

[name]

[contact]

E-mail: [[contact]](mailto:[contact]); [[contact]](mailto:[contact])

[name]

[contact]; [name]

E-mail: [[contact]](mailto:[contact]); [[contact]](mailto:[contact])

The PI notification to the Sponsor should then be updated in the eCRF or by written notification when new/additional information is available.

**Any fatal or life-threatening event should be reported immediately.** These preliminary reports will be followed as soon as reasonably possible by detailed descriptions that will include a completed SAE form, copies of hospital case reports, autopsy reports, and other documents, when requested and applicable.

If applicable, the investigator should also inform the representative of the appropriate IRB/Ethics Committee, as per the local requirements. A copy of the report cover letter should be filed within the study file.

### **9.8.2 Follow- Up of Serious Adverse Events**

Follow-up of SAEs that occur during the study will continue until their satisfactory resolution or stabilization.

If/when supplementary information is available, a follow-up SAE Report Form must be entered into the eCRF by the site or emailed within 24 hours to the Sponsor.

The contact information for follow up SAE reporting is the same as for initial SAE report (see above section).

Once e-mailed, the SAE form and accompanying documentation should be placed in the Safety section of the investigator's file. If supplementary information on a SAE has to be sent, the SAE form has to be used marked as 'follow-up report'.

A Post Approval Multicenter Open-label

Randomized Controlled Trial of Agili-C™ vs.

Surgical Standard of Care (SSOC) for the  
Treatment of Joint Surface Lesions of the Knee

CLN0021-US

Rev. 8

March 29, 2022

All other SAE/AEs will be followed for new information/resolution as possible, or may be defined as 'ongoing without further follow-up by the Investigator and Sponsor's decision.

## 9.9 Notification to Authorities

Events will be reviewed to determine any reporting obligations. Reporting will occur within the timelines described as per local regulations. Sponsor or designee will conduct and report the results of an evaluation to the appropriate authority and all participating investigators according to local regulations.

## 9.10 Anticipated Adverse Events Related to the Implant include:

- Transient or chronic pain and/or swelling and/or effusion of the operated joint
- Bone marrow edema
- Allergic or pseudo-allergic reaction and/or elevation of acute phase reactants
- Pseudo-septic reaction
- Reactive arthritis
- Bone cyst, bone fracture, bone deformities or bone aseptic necrosis
- Implant fracture, loosening or extrusion, with or without generation of particulate debris
- Abrasion of counter or nearby tissues
- Failure to induce tissue regeneration
- Tissue hypertrophy or intra-lesional bone formation
- Wound complications:
  - superficial or deep infections
  - septicaemia
  - wound dehiscence
  - hematoma or site drainage

- Intra-articular adhesions, hypertrophic tissue, hypertrophic synovitis, intra-articular adhesion, hypertrophic synovium or host reactions
- Inflammation of the joint and surrounding tissues
- Joint locking and limited range of motion, stiffness and arthritifibrosis
- Deep Vein Thrombosis
- Infection and related symptoms
- Elevation of the subchondral bone plate
- Degeneration of the surrounding cartilage
- Lack of cartilage integration
- Delamination
- Progression of degenerative changes and osteoarthritis
- Muscle atrophy

### **9.11 Anticipated Adverse Events – Related to tool-set include:**

- Postoperative hematoma
- Deformity or fracture of the bone
- Insertion of the tool can lead to a damage of nerve or vascular elements
- Heat damage to bone might occur especially with worn out drill bits
- Metal fragments might chip of the tools and lead to foreign body reaction
- Tool fragments might get stuck in the bone
- Failure to create an appropriate recipient site

## **10.0 Statistical Considerations**

### **10.1 Design Considerations**

This is a two-arm, post approval, open-label, randomized, multi-center study in which subjects are assigned to treatment (Agili-C™) or control (SSOC) in a 2:1 ratio.

The subjects in the study were randomized by site using variable block sizes.

A Post Approval Multicenter Open-label

Randomized Controlled Trial of Agili-C™ vs.

Surgical Standard of Care (SSOC) for the  
Treatment of Joint Surface Lesions of the Knee

CLN0021-US

Rev. 8

March 29, 2022

The subjects in the study will be stratified by extent of osteoarthritis, defined dichotomously by the Kellgren–Lawrence grade:

- Strata I: 0 & 1
- Strata II: 2 & 3

## 10.2 Analysis Populations

### 10.2.1 Safety Set

The safety population will consist of all patients for whom treatment with either Agili-C™ or SSOC was performed.

### 10.2.2 Full Analysis Set

The full analysis set (FAS) will consist of all treated subjects in the Agili-C™ arm and treated subjects in the SSOC arm, for whom there is a valid overall KOOS score at baseline and at least one valid overall KOOS score post-baseline.

Consistent with ICH-E9, subjects with major entry violations will be excluded from FAS. “Major” is defined by having the potential to affect trial results and the decision of whether an entry violation is considered major will be performed by the Medical Director.

FAS will be used for the primary analysis.

#### Treatment of missing data:

##### 1. KOOS Subscale Score:

As per KOOS scale guideline, subscale scores will be computed based on observed items only if not more than 2 items are missing. Where more than two items are missing, the KOOS subscale score will be scored missing.

##### 2. Overall KOOS Score:

	CLN0021-US-Investigational Plan A Post Approval Multicenter Open-label Randomized Controlled Trial of Agili-C™ vs. Surgical Standard of Care (SSOC) for the Treatment of Joint Surface Lesions of the Knee	Document Number: CLN-0000002 Document Version: 8.0 Effective Date: 08-Jun-2022 (GMT+2) Page 48 of 80 CLN0021-US Rev. 8 March 29, 2022
--	--	---

Overall KOOS Score will be defined as the average over the KOOS subscales, if not more than two subscales are missing. Where more than two KOOS subscales are missing, the Overall KOOS score will be scored missing.

### **10.3 Per Protocol Analysis Set (PP)**

The PP analysis set is the subset of FAS Subject with no major protocol violations and with valid observations on the primary endpoint (Overall KOOS) at 12 months, at least.

Treatment of missing data: missing data in the PP population will be dealt with using the same procedures described for FAS; i.e. subscale data will be scored as per user manual

### **10.4 Treatment of Efficacy Data Following a “Failure”**

For both Agili-C™ & SSOC groups, any secondary Invasive Intervention in the treated joint, regardless if related or unrelated to the original treatment, will be considered a Treatment Failure. Invasive Intervention includes: open procedure, mini-open procedure, arthroscopic procedure and any intra articular injections, such as: HA, PRP, steroids and stem cells.

Subjects who are treatment failures will have their subjective questionnaires (i.e. KOOS, IKDC, Tegner and SF-12 Health Survey) scores imputed as their baseline scores for analysis purposes.

For Agili-C™ group only:

- Failure to implant the device in indicated patients will be considered Treatment Failure. However failure to implant the device in contraindicated patient/condition will not be considered Treatment Failure. The latter subjects will not be included in the efficacy analyses.

	CLN0021-US-Investigational Plan A Post Approval Multicenter Open-label Randomized Controlled Trial of Agili-C™ vs. Surgical Standard of Care (SSOC) for the Treatment of Joint Surface Lesions of the Knee	Document Number: CLN-0000002 Document Version: 8.0 Effective Date: 08-Jun-2022 (GMT+2) Page 49 of 80
		CLN0021-US Rev. 8 March 29, 2022

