### **7.3.2 Final Screening/Procedure Visit (Visit 2)**

- Between 1 to 90 days after initial screening, subjects will undergo Final Screening (Visit 2) via arthroscopy. If found eligible, the subject will be enrolled into the study and randomized intra-operatively into either Agili-C™ or SSOC. Stratification will be performed based on K/L score performed off-site.
- For the SSOC group, lesion treatment will be determined according to subject's age, lesion size and K/L grade (Table 1) as per the control group selection algorithm (Figure 3).

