4.4 Safety Endpoint

Adverse events, including serious adverse events, reoperations and revisions, up to 24 months.

5 Treatment Failure Definition

- For both Agili-C™ & SSOC groups: any secondary invasive treatment in the treated joint, regardless if related or unrelated to the original treatment, will be considered a treatment failure. Invasive interventions include: open procedure, mini-open procedure, arthroscopic procedure and intra articular injections, such as: HA, PRP, stem cells and steroids.
- Additionally, for the Agili-C™ arm: failure to implant the device in indicated patients will be considered a treatment failure. However, failure to implant the device in contraindicated patients/conditions will not be considered a treatment failure.

6 Randomization

Subjects will be randomized to either receive the Agili-C™ device or the control arm SSOC in a 2:1 ratio. Subjects will be randomized by site using variable block sizes of 3 and 6.

7 Interim Analyses

Details for the interim analyses, decision criteria, models, imputation procedures, simulations and operating characteristics for the design are included in the Adaptive Design Report attached as Appendix 1. The interim analyses will be conducted by an independent statistician and reviewed by the Endpoint Adjudication Committee (EAC).

The interim analyses, as described in Appendix 1, include only the primary endpoint - change from baseline to 24 months in average overall KOOS score. For the EAC review, we will also summarize and test the first confirmatory secondary endpoint - change from baseline to 24 months in KOOS Pain subscore, using a Bayesian posterior probability of superiority. For this secondary confirmatory endpoint, the interim analysis will NOT include a longitudinal model to multiply impute incomplete observations. However, similarly to the primary outcome, we will consider any treatment failures to have the change from baseline to 24 months Pain subscore replaced with their baseline value. At the earlier interim analyses, there may be only a few

subjects that have reached 24-months of follow-up. If fewer than 30 subjects have completed follow-up at an interim analysis, no testing of the first confirmatory secondary endpoint will be performed and only descriptive statistics will be provided to the EAC.

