9.1 Analysis Populations

9.1.1 Full Analysis Set Population

The full analysis set (FAS) will consist of all treated subjects in the Agili-C™ arm and all treated subjects in the SSOC arm, for whom there is a valid overall KOOS score at baseline and at least one valid overall KOOS score post-baseline. A treated subject is defined as any subject who was randomized to any of the groups, and is not defined as a subject with major entry violation (as defined below).

In the FAS population, subjects who are treatment failures (as defined in Section 5.0) will have their 24-month KOOS score imputed as their baseline KOOS score. Thus, the treatment failure imputation will provide at least one valid overall KOOS score post-baseline and these subjects will be included in the primary analysis FAS population.

For all analyses performed on the FAS population, subjects will be analyzed according to the treatment arm to which they were randomized (regardless of the treatment actually received).

Consistent with ICH-E9, subjects with major entry violations will be excluded from FAS. Major entry violation is defined by having the potential to affect trial results and the decision of whether an entry violation is considered major will be performed by the Medical Director according to the following parameter - enrolment of subject with severe exclusion criteria, such as:

1. Bony defect depth deeper than 8mm
2. Uncontained lesion - lack of vital bone wall, at least 2mm thick, completely surrounding the lesion
3. Inability to position the implant 2mm recessed relative to the articular surface
4. Articular cartilage lesions in the tibia or the patella, ICRS grades IVa or above
5. Systemic cartilage and/or bone disorder

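### Protocol 10.4 removes some non-implanted Agili-C subjects from efficacy after randomisation, in one arm only; the SAP has no matching rule, and no analysis in the supplied text tests it (minor)

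*Protocol*

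**What the plan says.** **Protocol 10.4** has a part that applies to the Agili-C group only. Its first rule is that "Failure to implant the device in indicated patients will be considered Treatment Failure". Its second is that non-implantation in a contraindicated patient or condition is not a failure, followed by "The latter subjects will not be included in the efficacy analyses". There is no counterpart for SSOC. The section does not define *contraindicated* or say who decides.

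**Protocol 7.3.2** places allocation during surgery, once arthroscopy has confirmed eligibility: "the subject will be enrolled into the study and randomized intra-operatively into either Agili-C™ or SSOC". Protocol 10.1 describes the study as open-label.

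**Protocol 10.2.2** states: "The full analysis set (FAS) will consist of all treated subjects in the Agili-C™ arm and treated subjects in the SSOC arm". It also requires a valid baseline KOOS and "at least one valid overall KOOS score post-baseline", and it excludes major entry violations as judged by the Medical Director. It does not define *treated*.

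**SAP section 5** (Treatment Failure Definition) agrees that "failure to implant the device in contraindicated patients/conditions will not be considered a treatment failure" and stops there, with no removal from efficacy. **SAP 9.1.1** defines a treated subject as "any subject who was randomized to any of the groups, and is not defined as a subject with major entry violation". It analyses the FAS by randomised arm, whatever treatment was actually given.

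**The concern.** A rule that removes subjects after allocation, in one arm, in an open-label trial means that the groups compared at Month 60 may not be the randomised groups. A problem first noticed while an implant site is being prepared could not come to light in the same way in SSOC, where no site is prepared. Protocol 5.15 (bone wall violation during site creation) can be read as describing such a case, but the documents do not say that it occurred.

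Membership of the primary set is also unclear on paper. *Treated* in Protocol 10.2.2 cannot simply mean *implanted*, because 10.4 keeps non-implanted indicated subjects in the analysis as failures scored at baseline. The SAP's definition would keep the contraindicated subjects too, unless they were major entry violations. Protocol 10.4 would not.

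At stake is whether a reader can tell who was left out of the primary comparison, and whether the estimate depends on it.

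**Working it through.** **1. What each text does with a randomised, non-implanted, contraindicated Agili-C subject**

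| Text | Failure? | In efficacy? |
|---|---|---|
| Protocol 10.4 | No | No |
| Protocol 10.2.2 | not addressed | Depends on *treated* (undefined), a post-baseline KOOS and no major entry violation |
| SAP 5 | No | Not addressed |
| SAP 9.1.1 | not addressed | Yes, as randomised, given baseline and post-baseline KOOS, unless a major entry violation |

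**2. Does any analysis in the supplied text restore these subjects?** No. The per-protocol set (Protocol 10.3, SAP 9.1.3) is a subset of the FAS. The worst-case and tipping-point analyses (Protocol 10.10, SAP 9.3.1) vary missing values among subjects already in the analysis.

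**3. Reproducing the plan's power figures.** Inputs from Protocol 10.7.1: n = 120 and 59, SD 25, one-sided alpha 0.025, pooled t-test. SE = 25 × √(1/120 + 1/59) = 3.975. With the noncentral t distribution, power is 93.5% at 13.9 points (34.4 − 20.5) and 80.0% at 11.2 points. Both match the protocol. At 22.5 points the result is 99.99%, where the protocol states 99%.

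**4. Illustration of size.** The number affected, k, is not given, so it is an assumption here. Score k restored Agili-C subjects at baseline (change 0). A subject scored at baseline is never missing at Month 60, so all k count:

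- n₁ = 120 + k
- Agili-C mean M = 34.4 × 120 / (120 + k)
- difference = M − 20.5
- SE = 25 × √(1/n₁ + 1/59), with n₁ + 57 degrees of freedom

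The last column lets the SD grow with the added zeros. Pooled variance = [119 × 25² + 120 × (34.4 − M)² + k × M² + 58 × 25²] / (n₁ + 57). For k = 7 this gives an SD of 25.37.

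| k | n₁ | M | Difference | SE (SD 25) | Power (SD 25) | Power (SD inflated) |
|---|---|---|---|---|---|---|
| 0 | 120 | 34.40 | 13.9 | 3.975 | 93.5% | 93.5% |
| 1 | 121 | 34.12 | 13.6 | 3.970 | 92.7% | 92.6% |
| 7 | 127 | 32.50 | 12.0 | 3.939 | 85.8% | 84.8% |
| 10 | 130 | 31.75 | 11.3 | 3.924 | 81.4% | 79.9% |
| 11 | 131 | 31.51 | 11.0 | 3.920 | 79.8% | 78.1% |
| 12 | 132 | 31.27 | 10.8 | 3.915 | 78.2% | 76.3% |

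Power falls below 80% at k = 11 (k = 10 with the SD inflated). At k = 27 the expected difference is 34.4 × 120/147 − 20.5 = 7.58. With SE 3.853, t = 1.968 against a critical value of 1.972, so about 27 subjects bring the expected difference to the significance limit.

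The values 7 and 12 only set a scale. The number 12 is 251 − (160 + 79). The number 7 is two thirds of 251 (about 167) minus 160. Neither is a bound, for the reason given under the objection.

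**5. A milder assumption.** If the restored subjects improve like SSOC (20.5), the difference is (34.4 × 120 + 20.5k)/(120 + k) − 20.5. That gives 13.1 points at k = 7 and 12.6 at k = 12, with power 91.3% and 89.5% (SD 25).

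**6. Month 24.** With k subjects added at zero change, the reported difference of 22.5 becomes 43.0 × 160/(160 + k) − 20.5. That is 22.2 (k = 1), 20.7 (k = 7) and 19.5 (k = 12).

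**The case against.** **The group may be empty.** Eligibility is confirmed by arthroscopy before randomisation. Defect depth, containment and the ability to recess the implant can all be judged at that point. The major-entry-violation exclusion applies to both arms, and SAP 9.1.1 gives its list as examples, with the Medical Director deciding. Many contraindicated subjects could be removed that way. This stands, and it is the main reason for rating the point minor. What 10.4 alone removes is whatever remains, and the documents do not show that anything does.

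**The FAS has already been applied.** Protocol 10.7.1 reports 160 and 79 subjects at Month 24, and 10.7.4 says that FAS and PP differ by one Agili-C subject. Membership is therefore probably settled in practice. This also stands. The gap is that the number left out under 10.4, and the reasons, are not reported.

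**The supplied SAP is the 24-month plan.** This is true. It is nevertheless the only SAP supplied, and Protocol 10.5 carries forward the pivotal trial's models. The SAP refers to an Adaptive Design Report and the protocol to a Statistical Analysis Report. Neither was available, so step 2 above holds only for the supplied text.

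**Stronger readings that the documents do not support.**

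- *The rule favours the device.* It would do so only if the excluded knees did worse, which is not shown. The companion rule, which scores non-implanted indicated patients as failures, works against the device.
- *Twelve subjects were dropped.* The figure of 251 in Protocol 5.10 is an upper limit on pivotal enrollees still in follow-up, not the number randomised. Subtracting 239 from it does not count 10.4 exclusions.
- *The primary population must be redefined.* Month 24 results are known and the trial is open-label, so changing the primary set now would itself be a data-aware change.

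**Conclusion.** The point holds as a minor one. Protocol 10.4 contains a one-arm, post-randomisation exclusion that the SAP lacks, *treated* is undefined in the protocol, and nothing in the supplied protocol or SAP text shows whether the result depends on the rule.

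The existence of affected subjects, their number and the direction of bias are all unknown. The power figures are illustrations that rest on an assumed k, on zero change for restored subjects (unfavourable by design, since both documents say they are not failures) and on the protocol's own 13.9-point scenario. A reader might infer that the superiority conclusion is in doubt. At small k the documents' figures do not support that: one subject moves the expected difference from 13.9 to 13.6, and it takes about 27 to reach the significance limit. The effect to expect, if any, is a modest shift in the estimate.

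**What to change.** 1. Reconcile Protocol 10.4 and 10.2.2 with SAP 9.1.1 by stating what *treated* means and whether a non-implanted contraindicated subject is covered.
2. Report by arm the number of randomised subjects left out of the FAS and the reason for each, with 10.4 exclusions as a separate line. Protocol 10.6.2 and SAP 9.9 already plan the disposition tables, so this is an addition to them. Because these subjects come from the already enrolled pivotal trial, the count should be available now. If it is zero, one sentence closes the point.
3. If it is not zero, pre-specify before the Month 60 analysis a sensitivity run of the primary Bayesian model with these subjects included as randomised and without the post-baseline KOOS condition. Run it once with observed scores where available, and once with the non-implanted subjects scored at baseline. The second run is needed because model imputation for a subject with no post-baseline score borrows from that subject's own arm.

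The primary FAS used at Month 24 can stay as it is. The cost is a wording change, an addition to a planned table and at most two further model runs. The device estimate in those runs may be slightly less favourable.
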